10.3. Criteria for Treatment-Emergent Potentially Clinical Significant Value

Parameter	Treatment Emergent PCSV	Comments
Clinical Chemistry		
ALT*	
>3 and ≤ 5 ULN and baseline ≤ 3 ULN*
 
>5 and ≤ 10 ULN and baseline ≤ 5 ULN
 
>10 and ≤ 20 ULN and baseline ≤ 10 ULN
 
>20 ULN and baseline ≤ 20 ULN
	
Enzyme activity must be expressed in ULN, not in IU/L.
 
Concept paper on DILI – FDA draft Guidance Oct 2007.
 
Each category is calculated independently.
 
* At least one level is required, multiple levels are optional for phase 2/3 studies. If it is desirable to get the distribution across the different PCSV levels, additional shift table on ≤3, >3 to ≤5, > 5 to ≤10, >10 to ≤20, and > 20 category for baseline vs. post baseline may be provided

AST*	
>3 and ≤ 5 ULN and baseline ≤ 3 ULN*
 
>5 and ≤ 10 ULN and baseline ≤ 5 ULN
 
>10 and ≤ 20 ULN and baseline ≤ 10 ULN
 
>20 ULN and baseline ≤ 20 ULN
	
Enzyme activity must be expressed in ULN, not in IU/L.
 
Concept paper on DILI – FDA draft Guidance Oct 2007.
 
Each category is calculated independently.
 
* At least one level is required, multiple levels are optional for phase 2/3 studies. If it is desirable to get the distribution across the different PCSV levels, additional shift table on ≤3, >3 to ≤5, > 5 to ≤10, >10 to ≤20, and > 20 category for baseline vs. post baseline may be provided

Alkaline Phosphatase	>1.5 ULN and baseline ≤ 1.5 ULN	
Enzyme activity must be expressed in ULN, not in IU/L.
 
Concept paper on DILI – FDA draft Guidance Oct 2007.

Total Bilirubin*	
>1.5 and ≤ 2 ULN and baseline ≤ 1.5 ULN*
 
>2 ULN and baseline ≤ 2.0 ULN
	
Must be expressed in ULN, not in μmol/L or mg/L. Categories are cumulative.
 
Concept paper on DILI – FDA draft Guidance Oct 2007.
 
* At least one level is required, multiple levels are optional for phase 2/3 studies. If it is desirable to get the distribution of significant level, additional shift table on ≤1.5, >1.5 to ≤2.0 and > 2.0 category for baseline vs. post baseline may be provided

Parameter	Treatment Emergent PCSV	Comments
Conjugated Bilirubin	(Direct Bilirubin >35% Total Bilirubin and Total Bilirubin >1.5 ULN) and (Direct Bilirubin <=35% Total Bilirubin or Total Bilirubin <=1.5 ULN) at baseline	Conjugated bilirubin dosed on a case-by-case basis.
ALT and Total Bilirubin	(ALT>3 ULN and TBILI>2 ULN) and baseline (ALT <=3 ULN or TBILI <=2 ULN)	Concept paper on DILI – FDA draft Guidance Oct 2007.
CPK*	>3 and ≤ 10 ULN and baseline ≤ 3ULN* >10 ULN and baseline ≤ 10ULN	FDA Feb 2005. Am J Cardiol April 2006. Categories are cumulative. * At least one level is required, multiple levels are optional for phase 2/3 studies. If it is desirable to get the distribution of significant level, additional shift table on ≤3, >3 to ≤10, and > 10 category for baseline vs. post baseline may be provided
Creatinine	≥150 μmol/L (Adults) and baseline < 150 μmol/L >=30% change from baseline and <100% change from baseline ≥100% change from baseline	Benichou C., 1994. 3 independent criteria
Uric Acid		Harrison- Principles of internal Medicine 17 th Ed., 2008.
Hyperuricemia	>408 μmol/L and <=408 μmol/L at baseline	Two independent criteria
Hypouricemia	<120 μmol/L and >= 120 μmol/L at baseline	
Blood Urea Nitrogen	≥17 mmol/L and <17 mmol/L at baseline	Two independent criteria
Chloride		Two independent criteria
Hypochloremia	<80 mmol/L and baseline ≥ 80 mmol/L	
Hyperchloremia	>115 mmol/L and baseline ≤ 115 mmol/L	
Sodium		Two independent criteria
Hyponatremia	≤129 mmol/L and baseline > 129 mmol/L	
Hypernatremia	≥160 mmol/L and baseline <160 mmol/L	
Potassium		FDA Feb 2005.
Hypokalemia	<3 mmol/L and baseline ≥ 3 mmol/L	Two independent criteria
Hyperkalemia	≥5.5 mmol/L and baseline <5.5 mmol/L	
Total Cholesterol	≥7.74 mmol/L and < 7.74 mmol/L at baseline	Threshold for therapeutic intervention.
Triglycerides	≥4.6 mmol/L and < 4.6 mmol/L at baseline	Threshold for therapeutic intervention.

Parameter	Treatment Emergent PCSV	Comments
Glucose		
Hypoglycaemia	(≤ 3.9 mmol/L and $< LLN$) and (> 3.9 mmol/L or $\geq LLN$) at baseline	ADA May 2005.
Hyperglycaemia	≥ 11.1 mmol/L (unfasted); ≥ 7 mmol/L (fasted) and < 11.1 mmol/L (unfasted); < 7 mmol/L (fasted) at baseline	ADA Jan 2008.
HbA1c	$> 8\%$ and $\leq 8\%$ at baseline	
Albumin	≤ 25 g/L and > 25 g/L at baseline	
CRP	> 2 ULN or > 10 mg/L (if ULN not provided) and ≤ 2 ULN or ≤ 10 mg/L (if ULN not provided) at baseline	FDA Sept 2005.
Hematology		
WBC	< 3.0 Giga/L and ≥ 3.0 Giga/L at baseline (Non-Black); < 2.0 Giga/L and ≥ 2.0 Giga/L at baseline (Black) ≥ 16.0 Giga/L and < 16 Giga/L at baseline	Increase in WBC: not relevant. To be interpreted only if no differential count available.
Lymphocytes	> 4.0 Giga/L and ≤ 4.0 Giga/L at baseline	
Neutrophils	< 1.5 Giga/L and ≥ 1.5 Giga/L at baseline (Non-Black); < 1.0 Giga/L and ≥ 1.0 Giga/L at baseline (Black)	International Consensus meeting on drug-induced blood cytopenias, 1991. FDA criteria.
Monocytes	> 0.7 Giga/L ≤ 0.7 Giga/L at baseline	
Basophils	> 0.1 Giga/L ≤ 0.1 Giga/L at baseline	
Eosinophils	(> 0.5 Giga/L and $> ULN$) and (≤ 0.5 Giga/L or $\leq ULN$ at baseline)	Harrison- Principles of internal Medicine 17 th Ed., 2008.
Hemoglobin	≤ 115 g/L and > 115 g/L at baseline for male; ≤ 95 g/L and > 95 g/L at baseline for Female. ≥ 185 g/L and < 185 g/L at baseline for Male; ≥ 165 g/L and < 165 g/L at baseline for Female Decrease from Baseline ≥ 20 g/L	Three criteria are independent. Criteria based upon decrease from baseline are more relevant than based on absolute value. Other categories for decrease from baseline can be used (≥ 30 g/L, ≥ 40 g/L, ≥ 50 g/L).
Hematocrit	≤ 0.37 v/v and > 0.37 v/v at baseline for Male; ≤ 0.32 v/v and > 0.32 v/v at baseline for Female ≥ 0.55 v/v and < 0.55 v/v at baseline for Male; ≥ 0.5 v/v and < 0.5 v/v at baseline for Female	Two Criteria are independent

Parameter	Treatment Emergent PCSV	Comments
RBC	Female <3 Tera/L and baseline \geq 3 Tera/L \geq 6 Tera/L and baseline < 6 Tera/L Male <4 Tera/L and baseline \geq 4 Tera/L \geq 7 Tera/L and baseline < 7 Tera/L	Unless specifically required for particular drug development, the analysis is redundant with that of Hb. Otherwise, consider FDA criteria.
Platelets	<100 Giga/L and \geq 100 Giga/L at baseline \geq 700 Giga/L and < 700 Giga/L at baseline	International Consensus meeting on drug-induced blood cytopenias, 1991. Two independent criteria
Urinalysis		
pH	\leq 4.6 and > 4.6 at baseline \geq 8 and < 8 at baseline	Two independent criteria
Vital signs		
HR	\leq 50 bpm and decrease from baseline \geq 20 bpm \geq 120 bpm and increase from baseline \geq 20 bpm	To be applied for all positions (including missing) except STANDING.
SBP	\leq 95 mmHg and decrease from baseline \geq 20mmHg \geq 160 mmHg and increase from baseline \geq 20 mmHg	To be applied for all positions (including missing) except STANDING.
DBP	\leq 45 mmHg and decrease from baseline \geq 10 mmHg \geq 110 mmHg and increase from baseline \geq 10 mmHg	To be applied for all positions (including missing) except STANDING.
Weight	\geq 5% increase from baseline \geq 5% decrease from baseline	FDA Feb 2007.
ECG		Ref.: CPMP 1997 guideline.
HR	\leq 50 bpm and decrease from baseline \geq 20 bpm \geq 120 bpm and increase from baseline \geq 20 bpm	
PR	\geq 220 ms and increase from baseline \geq 20 ms	
QRS	\geq 120 ms & < 120 ms at baseline	

Parameter	Treatment Emergent PCSV	Comments
QTc	Absolute values (ms)	To be applied to any kind of QT correction formula.
Borderline	Borderline:	
Prolonged*	431-450 ms and < 431ms at baseline for Male;	
Additional	451-470 ms and < 451 ms at baseline for Female	
	Prolonged:	
	>450 to <500 ms and <= 450 ms at baseline for Male;	*QTc prolonged and Δ QTc>60 ms are the PCSA to be identified in individual subjects/patients listings.
	>470 to <500 ms and <= 470 ms at baseline for Female	
	\geq 500 ms and < 500 ms at baseline	5 independent criteria
	Increase from baseline	
	Borderline: Increase from baseline 30-60 ms	
	Prolonged: Increase from baseline >60 ms	

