#### 5.2.2.1. Reasons for Permanent Discontinuation of Study Drug

Patients will be permanently discontinued from study drug dosing in the event of:

- Anaphylactic reaction or other severe systemic reaction to study drug
- Diagnosis of a malignancy during study, excluding carcinoma in situ of the cervix, or squamous or basal cell carcinoma of the skin
- Pregnancy at any time during the study
- Any infection that is opportunistic, such as active tuberculosis and other infections whose nature or course may suggest an immuno-compromised status
- Severe laboratory abnormalities that are judged to be related to dupilumab per criteria described in Section 7.3.2, such as:
  - Neutrophil count  $\leq 0.5 \times 10^3/\mu\text{L}$
  - Platelet count  $\leq 50 \times 10^3/\mu\text{L}$
  - Confirmed (by 2 separate tests at least 2 weeks apart) alanine aminotransferase (ALT) and/or aspartate aminotransferase (AST) values  $>3 \times$  upper limit of normal (ULN) and total bilirubin  $>2 \times$  ULN, excluding confirmed Gilbert's Syndrome
  - Confirmed AST and/or ALT  $>5 \times$  ULN (for more than 2 weeks)
- Inadequate efficacy:
  - Patients who show inadequate therapeutic response after at least 12 weeks of treatment with dupilumab will be discontinued from the study treatment based upon review of the case and joint decision by the investigator and medical monitor. For the purpose of this assessment, a review of efficacy will be triggered whenever patients fail to achieve and/or maintain EASI-25 (at least 25% improvement in the EASI score) at week 16, compared to the baseline score in the previous controlled and/or short-term study. Patients may also withdraw from the study at any time if they are not satisfied with the study treatment (see Section 4.3)
- Other reasons that may lead to the permanent discontinuation of study drug include:
  - Certain AEs deemed related to the study drug (eg, severe and prolonged ISRs)

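### The SAP's only combined transaminase-plus-bilirubin row counts ALT but not AST, although the protocol's matching threshold levels use either enzyme

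*SAP*

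**What the plan says.** SAP 5.8 refers to Appendix 10.3 for the thresholds that define treatment-emergent potentially clinically significant values (PCSVs). In that appendix:

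- ALT and AST each have their own rows with identical bands, the lowest being ">3 and ≤ 5 ULN and baseline ≤ 3 ULN".
- One row combines a transaminase with total bilirubin, and AST is not in it: "ALT>3 ULN and TBILI>2 ULN) and baseline (ALT <=3 ULN or TBILI <=2 ULN". No reason is given for leaving AST out.
- For total bilirubin the lower category is ">1.5 and ≤ 2 ULN and baseline ≤ 1.5 ULN", and the comment beside it reads "Categories are cumulative". CPK carries the same comment, and its lower category runs from above 3 to 10 x ULN.

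Protocol 5.2.2.1 has a combined liver criterion among its reasons for permanent discontinuation. Its enzyme part is "alanine aminotransferase (ALT) and/or aspartate aminotransferase (AST) values" above 3 x ULN, joined to bilirubin above 2 x ULN ("upper limit of normal (ULN) and total bilirubin"). It falls under the heading "Severe laboratory abnormalities that are judged to be related to dupilumab per criteria described in Section 7.3.2". The finding must be "Confirmed (by 2 separate tests at least 2 weeks apart", and confirmed Gilbert's Syndrome is excluded. Protocol 5.2.2.2 refers back to the same list of severe abnormalities for cases where a link to dupilumab can reasonably be excluded.

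The protocol sets no PCSV thresholds of its own.

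**The concern.** The two documents use the same pair of cut-offs, but the SAP's version accepts only one of the two enzymes. Long-term safety is the primary objective, and a joint row exists to show that an enzyme rise and a bilirubin rise occurred in the same patient. Because the row is restricted to ALT, it can show zero while a patient has reached the protocol's AST and bilirubin levels. Separate AST and bilirubin counts do not reveal that they concern one person, so a reader of the summary tables would have to go to the listings to find out.

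The bilirubin and CPK categories raise a smaller, separate issue. A cumulative category above 1.5 x ULN and a band from above 1.5 to 2 x ULN give different counts. The table gives both instructions for the same row.

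**Working it through.** The documents state no figure on this point, so there is none to reproduce. The check is logical, with a small calculation for scale.

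**1. The rules, in multiples of ULN**

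- SAP row: ALT >3 and TBILI >2, with baseline ALT ≤3 or TBILI ≤2.
- Protocol levels only (setting aside confirmation, relatedness and Gilbert's Syndrome): (ALT >3 or AST >3) and TBILI >2.
- AST-inclusive row: (ALT >3 or AST >3) and TBILI >2, with baseline (ALT ≤3 and AST ≤3) or TBILI ≤2.

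In the SAP row the baseline clause is the logical complement of the post-baseline condition. The AST-inclusive clause keeps that structure.

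**2. Test profiles**

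ALT 2.5 or 4, AST 2.5, 4 or 6, and TBILI 1.2 or 2.5, with normal baseline, give 2 x 3 x 2 = 12 profiles. The six with TBILI 1.2 are negative under all three rules. The six with TBILI 2.5 are:

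| ALT | AST | SAP row | Protocol levels | AST-inclusive row |
|---|---|---|---|---|
| 2.5 | 2.5 | no | no | no |
| 2.5 | 4 | **no** | yes | yes |
| 2.5 | 6 | **no** | yes | yes |
| 4 | 2.5 | yes | yes | yes |
| 4 | 4 | yes | yes | yes |
| 4 | 6 | yes | yes | yes |

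The SAP row agrees with the protocol levels in 10 of 12 profiles, and both misses are AST-driven. The AST-inclusive row agrees in 12 of 12. In both missed profiles the patient is still counted in an AST row (above 3 to 5, or above 5 to 10) and in the bilirubin row above 2 x ULN.

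**3. Scale**

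SAP 2.2 gives 2678 enrolled patients. Assume that all are in the safety analysis set. The exact one-sided 95% upper limit for x cases is the 0.95 quantile of a Beta(x+1, 2678−x) distribution; for x = 0 it equals 1 − 0.05^(1/2678).

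| Cases in joint row | Proportion | Upper 95% limit |
|---|---|---|
| 0 | 0% | 0.11% |
| 1 | 1/2678 = 0.037% | 0.18% |
| 2 | 2/2678 = 0.075% | 0.23% |

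The documents do not give the number of AST-driven cases. The range 0 to 2 is illustrative.

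**4. Bilirubin bands**

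Take three patients with normal baseline: A peaks at 1.8, B goes straight to 3, and C has 1.8 and later 2.5 x ULN. Assume that any post-baseline value in a band counts.

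- Bounded, as coded: lower category A and C = 2; higher category B and C = 2.
- Cumulative, as commented: lower category A, B and C = 3; higher category B and C = 2.

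Nobody disappears, because B is in the higher category under both readings. The lower count does change, from 2 to 3. Adding the bounded rows does not recover the total: 2 + 2 = 4 for three patients, since C is in both. The same reasoning applies to CPK at 3 and 10 x ULN.

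**The case against.** The strongest reply is that these are not rival definitions of one quantity. The protocol text governs stopping of study drug and carries conditions that a descriptive screen does not have. The SAP is entitled to set its own PCSV thresholds. This stands. A reader might infer that the SAP row misses patients who meet the protocol's criterion, but the documents support only that it misses patients who reach its enzyme and bilirubin levels. The AST-inclusive row would not reproduce the full criterion either.

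A reader might also infer that an AST-driven case drops out of the report. It does not. SAP 5.8.2 provides a listing of all laboratory parameters with abnormality and PCSV flags by subject and visit, and the single-parameter rows keep the case. Patients who stop treatment early are listed with reasons (SAP 5.4), and adverse events leading to permanent discontinuation are tabulated (SAP 5.8.1). Only the joint summary count is missing.

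It is tempting to call this the key hepatic row, but the SAP does not rank its rows, and no PCSV row is an endpoint. The row also cites an outside concept paper and draft guidance. Whether that source uses ALT alone cannot be seen here, so no departure from it can be claimed.

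On the bilirubin and CPK bands, the reply is that no patient is lost and that the optional shift tables in the same cells use bounded bands, so the comment may be the error. That is a fair reading and leaves either correction open.

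None of this explains why AST is left out of the one row meant to link the two findings. Protocol 5.2.2.2 applies the same levels when causality is reasonably excluded, so they mark a severe abnormality whichever way relatedness is judged.

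**Conclusion.** The point holds as a misalignment with modest impact. The SAP's only joint transaminase-plus-bilirubin count is narrower on the enzyme than the protocol's own levels, and an AST-driven case would be absent from it. If all 2678 enrolled patients are in the safety set, one such case moves the row from 0% to 0.037%, and the upper limit from 0.11% to 0.18%. The true number of such cases is not in the documents and may be zero. No endpoint, sample size or test is affected, and the patient-level data remain in the report.

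The secondary point also holds as an internal conflict. For bilirubin and CPK, the lower-category count depends on whether the programmer follows the comment or the coded band. The stronger inference, that patients above the upper bound go uncounted, is wrong: they are counted in the higher category.

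**What to change.** In SAP 10.3, redefine the combined row as (ALT >3 ULN or AST >3 ULN) and TBILI >2 ULN, with baseline (ALT ≤3 ULN and AST ≤3 ULN) or TBILI ≤2 ULN, and retitle it to name both enzymes. If AST is left out on purpose, state the reason in the comment column.

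For total bilirubin and CPK, make comment and coding agree. Either delete the upper bounds of the lower categories, so that they read above 1.5 ULN and above 3 ULN, or keep the bounds and correct the comments. Either choice is sound if it is made before the tables are produced.

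The cost is an appendix edit and a small programming change on data already collected. The joint count may come out slightly higher. The one way it could fall is a patient who already has AST above 3 and bilirubin above 2 x ULN at baseline, with ALT at or below 3, and whose ALT later exceeds 3 with bilirubin still above 2. The matching baseline clause would treat that as pre-existing.

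No change to any discontinuation rule in the protocol is proposed.

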#### **6.3.2.4. Laboratory Testing**

Hematology, chemistry and serum pregnancy samples will be analyzed by a central laboratory.

Blood samples for serum chemistry testing will be collected to measure overall patient health at screening. Total basophil and eosinophil counts are of particular interest in AD patients, due to the occurrence of basophil histamine release and eosinophilia in this population. Understanding the lymphocyte profiles of AD patients may help researchers understand disease heterogeneity. Detailed instructions for blood sample collection are in the laboratory manual provided to study sites.

Samples for laboratory testing will be collected at time points according to Section 6.2. Tests will include:

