### 7.2.3. Other Events that Require Accelerated Reporting to Sponsor

The following events also require reporting to the sponsor (or designee) within 24 hours of learning of the event:

**Symptomatic Overdose of Study Drug:** Accidental or intentional overdose of at least 2 times the intended dose of study drug within the intended therapeutic window, if associated with an AE.

**Pregnancy:** Although pregnancy is not considered an AE, it is the responsibility of the investigator to report to the sponsor (or designee), within 24 hours of identification, any pregnancy occurring in a female patient during the study or within 12 weeks of the last dose of study drug. Any complication of pregnancy affecting a female study patient and/or fetus and/or newborn, must be reported as an SAE.

**Adverse Events of Special Interest:** AEs of special interest (AESIs) will be entered into the EDC system within 24 hours of identification. The site will also notify the Regeneron medical monitor of the AESIs within 24 hours of identification.

Adverse events of special interest in this study include:

- Anaphylactic reactions
- Systemic hypersensitivity reactions
- Helminthic infections
- Any severe type of conjunctivitis or blepharitis
- Keratitis
- Clinically symptomatic eosinophilia (or eosinophilia associated with clinical symptoms)

Additional AESIs for the sub-study using the new dupilumab drug product:

- Any serious or severe ISR or any ISR lasting longer than 24 hours.

Refer to the study reference manual for the procedures to be followed.

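### SAP 10.3 never counts further worsening in patients already past the single eosinophil, neutrophil or low-platelet PCSV level at baseline, and shows no depth for the rest

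*SAP*

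**What the plan says.** The hematology part of SAP 10.3 sets these criteria:

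- **Eosinophils.** The later value must be above 0.5 Giga/L and above ULN. The baseline condition is "and (≤ 0.5 Giga/L or" at or below ULN.
- **Neutrophils.** "< 1.5 Giga/L and ≥ 1.5 Giga/L at baseline (Non-Black); < 1.0 Giga/L and ≥ 1.0 Giga/L at baseline (Black". This is one level per race group.
- **Platelets, low side.** "<100 Giga/L and \geq 100 Giga/L at baseline". There is also one high-side level, at 700 Giga/L.

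None of these rows has a second severity level or a change-from-baseline criterion. Other rows of the same appendix do. ALT and AST have four levels, each with its own baseline condition, for example ">5 and ≤ 10 ULN and baseline ≤ 5 ULN". Total bilirubin and CPK have two levels. Creatinine and hemoglobin have criteria based on change from baseline, and the comment on hemoglobin rates that kind of criterion above an absolute one.

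SAP 5.8 takes the PCSV baseline from the current study. SAP 6.3 makes one exception, for a missing baseline. On why eosinophils matter, protocol 6.3.2.4 says: "Total basophil and eosinophil counts are of particular interest in AD patients, due to the occurrence of basophil histamine release and eosinophilia in this population".

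**The concern.** A baseline condition is what makes a PCSV treatment-emergent, so it is legitimate in itself. The difficulty comes from pairing it with only one level. A patient past that level on day 1 leaves the reach of the row for up to five years of treatment, whatever happens next. A patient who starts on the normal side is counted once, and a marginal crossing looks the same as an extreme one.

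The eosinophil row is where this matters most, because the protocol expects eosinophilia in these patients. The baseline is also that of the current study. For a patient who rolled over from a parent study with a count already raised, for whatever reason, the raised value sets the bar.

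The primary objective is long-term safety, and the PCSV row is a natural place for a reader to look for marked hematological change. A low count in that row could mean little worsening, or it could mean that the patients who worsened were not eligible to be counted. The table as planned cannot separate the two.

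**Working it through.** The plan states no figure to reproduce, so the check applies the rules as written.

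**1. The rules** (SAP 10.3; b = baseline, p = post-baseline, Giga/L)

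- Eosinophils: counted if p > 0.5 and p > ULN and (b ≤ 0.5 or b ≤ ULN). This is the same as p > max(0.5, ULN) and b ≤ max(0.5, ULN).
- Neutrophils: counted if p < t and b ≥ t, with t = 1.5 (non-Black) or 1.0 (Black).
- Low platelets: counted if p < 100 and b ≥ 100.

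Once b fails its condition, no value of p can make the rule true.

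**2. Cases.** The documents give no eosinophil ULN, so 0.4 to 0.7 is assumed.

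| Row | Baseline to later value | Counted? |
|---|---|---|
| Eosinophils | 0.49 to 0.75 | Yes, at every ULN tried |
| Eosinophils | 0.55 to 0.75 | No at ULN 0.4 or 0.5; yes at 0.6 or 0.7 |
| Eosinophils | 0.8 to 20 | No, at every ULN tried |
| Neutrophils, non-Black | 1.6 to 1.4 | Yes |
| Neutrophils, non-Black | 1.4 to 0.4 | No |
| Neutrophils, Black | 1.4 to 0.4 | Yes |
| Neutrophils, either group | 0.9 to 0.1 | No |
| Platelets | 101 to 99 | Yes |
| Platelets | 99 to 10 | No |

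The 0.55 case shows that a baseline above 0.5 but within ULN is not barred.

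**3. Depth.** For a non-Black patient, 1.6 to 1.4 and 1.6 to 0.4 both satisfy p < 1.5 with b ≥ 1.5. Each adds one to the same row.

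**4. Contrast within the appendix.** ALT going from 4 to 12 × ULN is counted in the >10 to ≤20 tier, because 4 ≤ 10. Male hemoglobin going from 110 to 85 g/L starts below the 115 g/L level but is counted by the fall: 110 − 85 = 25 ≥ 20.

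**5. Other laboratory summaries (SAP 5.8.2).** The count of newly abnormal values is limited to patients normal at screening and baseline. It therefore excludes the same eosinophil patients, who are above ULN by definition. For neutrophils and platelets the same follows if the lower limit of normal is not below the PCSV level. Shift tables are optional and described only as normal against abnormal, so a move within abnormal does not show. Visit-wise change summaries and graphs have no baseline restriction but are group-level. The by-patient listing shows every value.

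**6. Scale, eosinophils only.** SAP 2.2 gives 2678 enrolled. Baseline prevalence is not stated, so the share is an assumption:

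- 5%: 2678 × 0.05 ≈ 134
- 10%: 2678 × 0.10 ≈ 268
- 30%: 2678 × 0.30 ≈ 803
- 50%: 2678 × 0.50 = 1339

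These are patients who could not be counted, not patients who worsened.

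**7. Effect of tiers.** Add neutrophil tiers at ≤1.0 and ≤0.5 with baseline above each. The non-Black fall from 1.4 to 0.4 is then counted at both. Add a platelet tier at ≤50 with baseline above 50, and 95 to 45 is counted. For eosinophils, any tier T with 0.8 ≤ T < 20 counts the move from 0.8 to 20.

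**The case against.** The strongest reply is that this is how a treatment-emergent PCSV is meant to work, and that the PCSV table is one summary among several, produced depending on data. The worsening is not lost. It is in the listing, it enters the change-from-baseline statistics, and worsening of a preexisting condition is an adverse event under protocol 7.1.1 when clinically significant. The contrast with ALT, AST, bilirubin and CPK is also softer than it looks, because the comments on those rows require one level and make further levels optional. All of this stands. It limits the point to an insensitivity in one table. It does not remove it, because no committed summary table shows how many patients who were abnormal at baseline became markedly worse.

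Three stronger readings are tempting, and the documents do not support them.

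- A reader might infer that falls to the protocol's discontinuation levels are hidden in general. They are not. A patient normal at baseline who falls to neutrophils 0.4 or platelets 45 is counted; only the depth is missing. Platelets below 100, and neutrophils below 1.0 in Black patients, already have rows.
- A reader might infer that capture of the adverse event of special interest "Clinically symptomatic eosinophilia (or eosinophilia associated with clinical symptoms" is impaired. That is a clinical event reported by the investigator and does not derive from the PCSV row. It also entered with amendment 9, whereas SAP version 2.0 rests on amendments 6 to 8.
- A reader might infer a number of patients with marked eosinophilia missing from the table. The documents give neither the baseline share nor a rate of progression. They also do not show that the barred patients are those at highest risk.

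**Conclusion.** The point holds in limited form. With one level and a baseline condition at that same level, the eosinophil, neutrophil and low-platelet rows cannot register worsening from an already abnormal baseline, and they do not grade worsening from a normal one. This follows from the wording and needs no assumption, except that for eosinophils the barred group is those above both 0.5 Giga/L and ULN.

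The size is unknown. The range of about 134 to 1339 patients illustrates assumed shares of 5% to 50% and is not an estimate. It also uses enrolled rather than treated patients. For neutrophils and platelets the documents give nothing on how many start low. The case for acting rests mainly on eosinophils, on the long-term safety objective, and on the low cost.

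**What to change.** In the next SAP version or addendum, add reporting tiers to SAP 10.3. Count each tier independently and give each its own baseline condition, as in the ALT and AST rows.

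- **Neutrophils:** ≤0.5 for all patients and ≤1.0 for non-Black patients.
- **Platelets:** ≤50.
- **Eosinophils:** at least one higher reporting level chosen by the sponsor's medical lead, or a multi-category shift table of baseline against worst post-baseline value.
- **All three rows:** the number of patients already past the lowest level at baseline. State whether they stay in the percentage denominator, which SAP 5.8.2 does not specify.

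The neutrophil and platelet levels are those already named in protocol 5.2.2.1 and 5.2.2.2 (10^3/µL is the same unit as Giga/L). All tiers are for reporting only and change no clinical rule. A patient past the highest tier at baseline would still not be counted as worsening, which is why the baseline count or the shift table is needed as well.

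The cost is appendix wording and a few table rows on data already collected. Protocol section 9 allows the SAP to be revised before database lock, and SAP section 7 foresees addenda for later analyses.
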